2.9.5.1. Adverse Events

Frequency tables for the preferred terms will be compiled, based on patients experiencing an AE and based on the number of AEs. The AE will also be analysed with regard to system organ class. They will be displayed with regard to severity and relationship to study drug. All AEs will be listed.

2.9.5.2. Criteria for clinically notable laboratory abnormalities

Please note: Normal ranges are given by the central laboratory of the University Hospital Erlangen-Nuremberg

Liver parameters:

Serum SGOT, SGPT, γ -GT, AP > 30% of upper normal range

Renal parameters:

decrease of eGFR (CKD-Epi) >30%, serum potassium above normal range, serum sodium under normal range

Hematological parameters:

Abnormal blood cell counts at baseline and changes of $\geq 20\%$ of blood cell counts

Descriptive statistics of all laboratory values will be given.

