2.8. Safety and Tolerability Measures

Term	Definition
Adverse Event (AE) Ref: ISO 14155-2011	Any untoward medical occurrence, unintended disease or injury, or untoward clinical signs (including abnormal laboratory findings) in subjects, users or other persons, whether or not related to the investigational medical device. NOTE 1: This definition includes events related to the investigational medical device or the comparator. NOTE 2: This definition includes events related to the procedures involved NOTE 3: For users or other persons, this definition is restricted to events related to the investigational medical device.
Adverse Device Effect (ADE) Ref: ISO 14155-2011	AE related to the use of an investigational medical device NOTE 1: This definition includes adverse events resulting from insufficient or inadequate instructions for use, deployment, implantation, installation, or operation, or any malfunction of the investigational medical device. NOTE 2: This definition includes any event resulting from use error or from intentional misuse of the investigational medical device.
Serious Adverse Event (SAE) Ref: Ordinance on Medical Devices Vigilance (MPSV)	Adverse event that directly or indirectly have led, might have led, or might lead to death or to a serious deterioration in the health of a subject, user, or other person, whether or not related to the investigational medical device,
Serious Adverse Device Effect (SADE) Ref: ISO 14155-2011	Adverse device effect that has resulted in any of the consequences characteristic of a SAE.
Unanticipated Serious Adverse Device Effect (USADE) Ref: ISO 14155-2011	Serious adverse device effect which by its nature, incidence, severity, or outcome has not been identified in the current version of the risk analysis report. NOTE 1: Anticipated serious adverse device effect (ASADE) is an effect which by its nature, incidence, severity or outcome has been identified in the risk analysis report.
Device Deficiency Ref: ISO 14155-2011	Inadequacy of a medical device with respect to its identity, quality, durability, reliability, safety or performance. NOTE: Device deficiencies include malfunctions, use errors, and inadequate labelling.

Definitions of Adverse Events and Device Deficiency

Assessment of Severity

The clinical severity of an AE will be classified as:

Mild: asymptomatic or mild symptoms; clinical or diagnostic observations only; intervention not indicated.

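### Two laboratory flags in SAP 2.9.5.2 are wrong as worded: normal values meet the liver limit, and the haematology line has no criterion for a count that becomes abnormal after the procedure

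*SAP*

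**What the plan says.** SAP 2.9.5.2 takes its reference limits from one source: "Normal ranges are given by the central laboratory of the University Hospital". No numerical limits are printed. It then lists three groups of criteria.

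- **Liver** (SGOT, SGPT, γ-GT, AP): "AP > 30% of upper normal range".
- **Renal:** a fall in eGFR of more than 30%, and "serum potassium above normal range, serum sodium under normal range".
- **Haematology:** "Abnormal blood cell counts at baseline and changes of" at least 20% "of blood cell counts".

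The section closes with "Descriptive statistics of all laboratory values will be given". The laboratory table in SAP 2.7.3.1 lists haemoglobin and haematocrit as items separate from the erythrocyte, platelet and white cell counts. SAP 2.2 names laboratory abnormalities that investigators judge related to RDN among the main bases of the safety assessment.

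**The concern.** A notable-abnormality criterion should pick out patients whose values became abnormal, or moved materially, after the intervention. The renal criteria do this: each is a fall or a value beyond a stated limit, and none depends on the baseline being abnormal. The other two lines do not.

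The liver line sets its threshold as a percentage *of* the upper limit, not a percentage *above* it. The haematology line ties the flag to an abnormal baseline count and never mentions a count that becomes abnormal afterwards. It gives no direction of change. Read strictly, it also leaves haemoglobin and haematocrit without any criterion.

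What is at stake is whether individual patients with a new laboratory abnormality can be identified by a reproducible rule. Two programmers working from this text could flag very different sets of patients from the same data.

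**Working it through.** The plan gives no figure to reproduce here. The check applies each criterion as written to test values scaled to the laboratory limits, because the SAP prints no numerical ULN or lower limit of normal (LLN).

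**Liver.** The input is the criterion in SAP 2.9.5.2. The literal rule is value > 0.30 × ULN. The probable intention is value > 1.30 × ULN.

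| Value (× ULN) | Literal rule | > 1.30 × ULN |
|---|---|---|
| 0.25 | no | no |
| 0.31 | flagged | no |
| 0.50 | flagged | no |
| 1.00 | flagged | no |
| 1.20 | flagged | no |
| 1.31 | flagged | flagged |

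With an illustrative ULN of 40 U/L (an assumption), the literal threshold is 0.30 × 40 = 12 U/L.

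To gauge how many healthy values this would catch, assume that they are log-normal with the ULN at the 97.5th percentile and log-SD *s*. In units of ULN the log-mean is −1.96*s*, so P(value > c × ULN) = 1 − Φ((ln c + 1.96*s*)/*s*).

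- *s* = 0.3, c = 0.3: (−1.204 + 0.588)/0.3 = −2.05, giving 98%.
- *s* = 0.6, c = 0.3: (−1.204 + 1.176)/0.6 = −0.05, giving 52%.
- *s* = 0.3, c = 1.3: (0.262 + 0.588)/0.3 = 2.83, giving 0.2%.
- *s* = 0.6, c = 1.3: (0.262 + 1.176)/0.6 = 2.40, giving 0.8%.

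The distribution and the range of *s* are assumptions. The logical point, that values within the limit meet the rule, does not depend on them.

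**Haematology.** The inputs are the two conditions in SAP 2.9.5.2. The change is (after − before)/before. For these examples the ULN is set at 2.5 × LLN (an assumption). *Joint* means that both conditions are required; *separate* means that either suffices.

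| Before → after (× LLN) | Change | Newly out of range | Joint | Separate |
|---|---|---|---|---|
| 1.10 → 0.95 | −13.6% | yes | no | no |
| 1.26 → 0.90 | −28.6% | yes | no | flagged |
| 2.0 → 0.5 | −75.0% | yes | no | flagged |
| 0.9 → 0.9 | 0% | no | no | flagged |
| 0.8 → 1.0 | +25.0% | no, a recovery | flagged | flagged |
| 2.0 → 1.5 | −25.0% | no | no | flagged |

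Under the joint reading none of the three new abnormalities is flagged, whatever the size of the fall, while the recovery is. Under the separate reading the two larger falls are caught, but the 13.6% fall below the limit is not, and an unchanged pre-procedure abnormality is. Neither reading contains a criterion for a count that newly leaves the range.

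**The case against.** The liver line is most naturally read as shorthand for 30% above the limit, since a section on abnormalities cannot mean to flag normal values. That is fair as to intention. But the text says otherwise and no other section corrects it, so the intended multiple has to be stated.

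The haematology line may be meant as two items. A large fall from a normal baseline is then flagged, and leaving smaller boundary crossings unflagged is a choice about what counts as notable. This stands in part: on that reading the gap is confined to changes under 20%. The first item would still describe only the state before the procedure.

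The plan also has other routes. Laboratory values are summarised descriptively (SAP 2.2 and 2.9.5.2). The adverse event definition covers "untoward clinical signs (including abnormal laboratory findings) in subjects", and all adverse events are listed (2.9.5.1). Vascular and access-site complications are reported separately (1.1.5). These limit the consequence. They do not repair the criteria, because group summaries do not identify individual patients and adverse event capture depends on what the investigator records.

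A reader might go further and infer any of the following, none of which the SAP supports:

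- **That all the laboratory flags are faulty.** The renal ones are soundly worded.
- **That large falls from a normal baseline are certainly missed.** That follows only from the joint reading.
- **That a fall in haemoglobin shows the effect of the *and*.** Haemoglobin is listed apart from the cell counts, so whether the criterion covers it at all is unclear.
- **That patients will drop out of a planned safety table.** SAP 2.9.5.2 specifies no table or group comparison built on these flags.

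**Conclusion.** The point holds for the liver and haematology criteria only. The liver wording is literally met by values from just over 0.3 up to 1.0 times ULN. On the assumed distributions that is roughly half to nearly all healthy values, against under 1% for a limit of 1.3 times ULN. This matters only if the text is programmed literally.

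The haematology wording has no criterion for a new post-procedure abnormality on either reading. The size of the gap depends on the reading: every patient with normal baseline counts if the conditions are joint, and only changes below 20% if they are separate.

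This is a minor point. It touches descriptive safety reporting in a trial whose analysis SAP 2.4 already calls exploratory and descriptive. No efficacy result or type I error is affected.

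**What to change.** Reword two lines of SAP 2.9.5.2.

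- **Liver:** give the limit as an explicit multiple of ULN: > 1.3 × ULN if 30% above the limit is meant, which the sponsor should confirm.
- **Haematology:** apply the flag to post-procedure values. Flag a count that is outside the laboratory's normal range when it was inside before the procedure, *or* a change of at least 20% from baseline whatever the baseline status. Name the parameters covered, including whether haemoglobin is one of them, and state the direction of change. Without a stated direction, the recovery from 0.8 to 1.0 × LLN would still be flagged.

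These are reporting definitions and do not alter how any patient is managed. The cost is two lines of text, the matching code and a few more haematology values to list.

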2.9.6. Vital signs

Descriptive statistics of all vital signs will be produced.

2.9.7. Electrocardiogram

Descriptive statistics will be produced, if applicable.

2.9.8. Physical examination

Descriptive statistics will be displayed, if applicable.

2.9.9. Subgroup analysis

Will be defined once the baseline characteristics and discrepancies are known. Most important subgroup analysis would be to compare all primary and secondary objectives (1.1.1 – 1.1.5) between patients with CKD 3a (eGFR=45-59; creatinine derived eGFR calculated based on CKD-epi formula) and 3b (eGFR=30-44; creatinine derived eGFR calculated based on CKD-epi formula)

